During the dose-escalation phase, up to 4 courses may be administered. In case of evidence of clinical benefit as judged by the investigator (e.g. PR, CR, disease stabilization, amelioration of CLL related symptoms), treatment with BI 836826 can be continued for another 4 courses after discussion between the Investigator and the Clinical Monitor of the sponsor. During treatment of the expansion cohort, a maximum of 8 courses may be offered to all patients. In the dose-escalation phase as well as in the expansion cohort, in patients who experience sustained benefit and tolerate treatment well, treatment may be continued beyond 8 courses on a case by case basis after discussion between the Investigator and the Clinical Monitor of the sponsor. If patients continue beyond cycle 8, the same assessments will be done as applicable for cycles 5-8. At the end of each treatment course, adverse events and safety laboratory will be assessed. To continue treatment with further courses, **all** of the following criteria must be met:

(1) Neutrophils  $\geq 500 \ /\mu L \ (0.5 \ x \ 10^9/L)$  and platelets  $\geq 25.000 \ /\mu L \ (25 \ x \ 10^9/L)$ , with or without growth-factor support or transfusions.

(2) Acceptable tolerability (in case of an adverse event at the planned start of a treatment course, patients may continue therapy only after recovery to a level which would allow further therapy, i.e. CTCAE grade 1 or pre-treatment value.)

In case criterion 1 and/or 2 is not fulfilled, blood counts and/or the adverse event should be re-evaluated for up to three weeks. Any case of a delay in treatment course should be communicated to the Clinical Monitor at Boehringer Ingelheim. As soon as criterion 1 is met, the investigator in agreement with the Clinical Monitor at Boehringer Ingelheim may continue the treatment (unless other criteria for discontinuation or withdrawal apply, see Section 3.3.4.1). In case an adverse event is continuing at a CTCAE grade 2 or higher without recovery to grade 1 within 5 weeks after the last BI 836826 infusion and this is above the pre-treatment level, the investigator in agreement with the Clinical Monitor at Boehringer Ingelheim may continue BI 836826 only in the case that the event is considered not drug-related by investigator and sponsor.

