#### Protocol-specified significant adverse event

A significant adverse event is defined as an adverse event which is of particular concern for safety monitoring within this trial. These adverse events need to be handled by the investigator according to the rules defined for SAE reporting. "Significant" in this context is a regulatory term that is not related to a clinical assessment. Based on preclinical data and experience with other monoclonal antibodies significant adverse events defined for this trial are:

- Infusion-related reactions (CTCAE grade 3 or higher),
- Tumour lysis syndrome,
- Any event that qualifies for DLT,
- Drug-induced liver injury (DILI)
  - Although rare, DILI is under constant surveillance by sponsors and regulators and is considered a protocol-specified significant adverse event. Timely detection, evaluation, and follow-up of laboratory alterations of selected liver laboratory parameters to

distinguish an effect of the underlying malignancy on liver function from other causes such as DILI are important for patient safety. The following are considered as Protocolspecified significant events:

Hepatic injury defined by the following alterations of liver parameters:

- For patients with normal liver function (ALT, AST and bilirubin within normal limits) at baseline an elevation of AST and/or ALT ≥3 fold ULN combined with an elevation of bilirubin ≥2 fold ULN measured in the same blood draw sample. Patients showing these lab abnormalities need to be followed up according to Appendix 10.5 of this clinical trial protocol and the "DILI checklist" provided in the ISF.
- For patients with impaired liver function at baseline an elevation of AST and/or ALT >5 fold ULN combined with an elevation of total bilirubin >2 fold ULN measured in the same blood draw sample. Patients showing these lab abnormalities need to be followed up according to Appendix 10.5 of this clinical trial protocol and the "DILI checklist" provided in ISF.

Protocol-specified significant adverse events are to be reported in an expedited manner similar to Serious Adverse Events, even if they do not meet any of the seriousness criteria - for details see section 5.2.2.2. If the investigator determines any protocol-specific significant adverse event is related to study drug, the administration of the study drug must be managed according to section 4.1.4 of the protocol.

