#### 5.2.3 Assessment of safety laboratory parameters

5.2.3.1 General safety laboratory parameters

Blood samples and urine have to be collected at the time points specified in the Flow Chart. Blood samples should be collected more frequently in case of relevant toxicities; e.g. in case of grade 4 neutropenia or thrombocytopenia, to document as accurately as possible the duration of the AE. Safety laboratory examinations will include haematology, biochemistry, coagulation and qualitative urine analysis:

Haematology	Haemoglobin, red blood cell count (RBC), white blood cell count (WBC) with differential, platelets (PLT)
	Reticulocytes have to be measured only at Screening, Visit 1, Day 1 of each treatment course, at the EOT visit and during follow-up.
Biochemistry	Glucose, sodium, potassium, calcium, inorganic phosphate, creatinine, aspartate amino transferase (AST), alanine amino transferase (ALT), alkaline phosphatase (AP), lactate dehydrogenase (LDH), total bilirubin (if elevated provide direct bilirubin), urea, total protein, albumin, uric acid
	Serum immunoglobulin levels (IgG, IgM, IgA), direct antiglobulin test have to be measured only at Screening, Visit 1, Day 1 of each treatment course, at the EOT visit and during follow-up.
Coagulation	Activated partial thromboplastin time (aPTT), prothrombin time (PT), international normalised ratio (INR) where indicated (e.g. treatment with vitamin K antagonists)
Urine	pH, glucose, erythrocytes, leukocytes, protein, nitrite will be analysed by dipstick and reported as semiquantitative measurements. In case of pathological findings, further evaluation should be performed and results documented.
Pregnancy test	A serum pregnancy test needs to be obtained at the time points indicated in the Flow Chart in patients of childbearing potential.

In case a treatment course is delayed due to an adverse event, the patient should visit the site at least once a week for assessment of safety laboratory and adverse events. More frequent visits may be appropriate as assessed by the investigator.

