### 6.2.2 Treatment periods

#### 6.2.2.1 Visit 1 - day 1 (day 1 of a treatment course)

On the treatment days, the following parameters and investigations will be obtained and / or performed:

- Review of inclusion and exclusion criteria (patient eligibility), in the first cycle only
- Blood samples for pharmacogenetic investigations (optional, only after signature of separate informed consent)
- Physical examination, weight
- Vital signs at time points specified in Section 5.2.5.1
- Adverse events (AEs)
- Changes in concomitant therapies
- Administration of BI 836826 after final confirmation of dose tier
- Safety lab parameters before trial drug administration as specified in Section 5.2.3.1
- •
- Blood samples to screen for evidence of tumour lysis syndrome (see Section 5.2.3.2)
- Serum pregnancy test in women of childbearing potential (does not have to be repeated in case pregnancy test has been performed within the last 3 days)
- CMV monitoring (see Section 5.2.3.3.2)

- •
- Response assessment (blood and clinical assessment) at the end of each treatment course prior to next administration of BI 836826, may be performed at day 1 of the next course prior to treatment administration or up to 1 day earlier to allow for a timely continuation of the treatment.
- Assessment of eligibility for further courses in all treatment courses except for course 1

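### Protocol 4.1.4: the sentence on resuming a delayed course names only the blood-count criterion and, read literally, conflicts with the rule that adverse events must also have recovered (minor)

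*Protocol*

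**What the plan says.** Protocol Section 4.1.4 says that all of the listed criteria must be met before a further course.

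- **Criterion 1:** neutrophils of at least 0.5 x 10^9/L and platelets of at least 25 x 10^9/L, with growth factors or transfusions allowed.
- **Criterion 2:** if an adverse event is present at the planned start of a course, "patients may continue therapy only after recovery to a level which would allow further therapy, i.e. CTCAE grade 1 or pre-treatment value".

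The next paragraph deals with delays. It opens: "In case criterion 1 and/or 2 is not fulfilled, blood counts and/or the adverse event should be re-evaluated for up to three weeks". It then says: "As soon as criterion 1 is met, the investigator in agreement with the Clinical Monitor at Boehringer Ingelheim may continue the treatment". That permission carries one exception, which points to the withdrawal and discontinuation rules in Section 3.3.4.1. The last sentence concerns an event of grade 2 or higher, above the pre-treatment level, "without recovery to grade 1 within 5 weeks after the last BI 836826 infusion". Treatment may then continue only if investigator and sponsor both judge the event not drug-related.

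A separate paragraph of Section 4.1.4 requires recovery from a DLT to grade 1 or the pre-treatment value.

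**The concern.** The delay paragraph admits patients held for counts, for an adverse event, or for both, but its release condition mentions counts only. A patient held solely for an adverse event already satisfies criterion 1, so on the literal wording that patient could be released at once. The all-criteria rule a few lines above says the opposite.

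At stake is whether this first-in-human protocol has one clear rule on re-dosing a patient with an unresolved drug-related event. Other parts of the protocol rely on this section. For related protocol-specified significant events, Section 5.2.2.1 says that "the administration of the study drug must be managed according to section 4.1.4 of the protocol".

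**Working it through.** No sample size, power or error rate is involved. The check sets the rules side by side and asks, for each kind of patient, whether they agree.

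**Case by case**

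1. *Counts too low, no other event.* Criterion 1 holds the patient and the release sentence frees the patient when counts recover. The rules agree.
2. *Counts adequate; an unresolved drug-related event of grade 2 or higher, above pre-treatment level, not a DLT; less than 5 weeks since the last infusion.* The all-criteria rule and criterion 2 forbid the next course. The release sentence, read literally, permits it. The rules conflict.
3. *The same event still unresolved at 5 weeks.* The last sentence of the paragraph bars continuation because the event is drug-related. The rule is clear.
4. *A DLT.* The separate DLT paragraph requires recovery. The rule is clear.

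The conflict is confined to case 2.

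**Does another rule settle case 2?**

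- The exception in the release sentence points to Section 3.3.4.1. The only item there on recovery from drug toxicity is a DLT that does not recover.
- Section 5.2.1.1 sets the non-haematological DLT threshold at grade 3, so a grade 2 event falls outside the DLT rule. Among anaemias, only grade 4 is listed as a DLT, and criterion 1 does not measure haemoglobin.
- Section 6.2.2.1 lists "Assessment of eligibility for further courses in all treatment courses except for course 1", and the Flow Chart for Courses 2 - 8 has a matching row. Neither restates the criteria, so both lead back to Section 4.1.4.

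Before 5 weeks, criterion 2 is therefore the only express bar, and it is the rule that the release sentence omits.

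**Where the window lies**

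Count the first infusion of a course as day 1. With 14-day courses, the next planned start is day 15.

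- End of re-evaluation: 15 + 21 = day 36.
- 5-week mark = day of last infusion + 35. Last infusion on day 1: 1 + 35 = day 36. On day 2: 2 + 35 = day 37. On day 8: 8 + 35 = day 43.

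The 5-week mark falls 0, 1 or 7 days after re-evaluation ends, so case 2 can arise at any point up to the end of re-evaluation. The day 2 and day 8 figures apply to course 1, and to course 2 if the DSMB supports splitting the dose there (Section 4.1). These dates show where the ambiguity applies. They do not measure how often it would matter.

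**A related tension**

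Exclusion criterion 10 requires neutrophils of at least 1.0 x 10^9/L at entry, while criterion 1 accepts 0.5, and 0.5 / 1.0 = 50%. A patient who entered at 1.0 and is now at 0.6 meets criterion 1 but is below the pre-treatment value. If that neutropenia is recorded as an adverse event, criterion 2 read strictly still holds the patient. The sponsor may have intended counts to be governed by criterion 1 alone, but the text does not say so.

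**The case against.** The strongest reply is that nothing is contradicted. The all-criteria rule and criterion 2 are mandatory. The release sentence is permissive, needs the Clinical Monitor's agreement, and nowhere says that criterion 1 alone suffices, so both can be obeyed together. The paragraph can also be read as two tracks: the release sentence closes the blood-count track and the 5-week sentence closes the adverse-event track. The literal reading has an odd result as well, since it would allow early what is forbidden at 5 weeks.

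Much of this stands, and it makes criterion 2 the probable intent. It does not remove the defect. The sentence follows an opening that expressly includes patients held for criterion 2, and the reader has to supply a limit that the text omits. The Clinical Monitor works from the same text, and agreement is a safeguard, not a recovery criterion.

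Infusion-related reactions are a tempting example, because Section 5.2.1.1 excludes them from DLT and Section 5.2.2.1 sends related reactions of grade 3 or higher to Section 4.1.4. The example is weak. Section 4.1 has its own stop-and-resume rule within an infusion, and the documents give no reason to expect a reaction to persist until the next course, about two weeks later.

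Other safeguards limit exposure. Section 5.2.3.1 says: "In case a treatment course is delayed due to an adverse event, the patient should visit the site at least once a week". A full 21-day delay would therefore include at least 21 / 7 = 3 visits, and a shorter one fewer.

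**Conclusion.** The point holds as a minor wording conflict in an operative dosing rule. It affects one group: patients less than 5 weeks from the last infusion with an unresolved drug-related event that is not a DLT, chiefly grade 2 non-haematological events or anaemia below grade 4. The documents give no frequency for such events, so the number of patients cannot be estimated.

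A reader might infer two stronger things that the documents do not support.

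- *That the protocol sets out to re-dose through toxicity.* Criterion 2, the all-criteria rule and the 5-week sentence all point the other way.
- *That the MTD determination is compromised.* Section 5.2.1.1 and SAP Section 5.1 base it on DLTs in the first course, before any resumption decision arises. DLT-type events in later courses do inform confirmation of the MTD and the choice of expansion dose, but nothing in the documents shows that this wording would distort them.

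The conclusion assumes only that the sentence is read as printed.

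**What to change.** Change the opening condition of the release sentence to *As soon as criteria 1 and 2 are both met* and leave the rest as it stands. State that the 5-week sentence is the exception to criterion 2, for events that investigator and sponsor both judge not drug-related.

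If the sponsor intends neutrophil and platelet counts to be governed by criterion 1 alone (0.5 and 25 x 10^9/L), this should be written into criterion 2 itself. There would then be two explicit and consistent exceptions: counts under criterion 1, and unrelated events at 5 weeks. Placing the count exemption only in the release sentence would leave criterion 2 contradicting it. Such an exemption would be a deliberate choice for the sponsor to justify, not a mere clarification. The DLT paragraph needs no change.

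The cost is a short protocol clarification. The downside is an occasional longer delay, which criterion 2 already demands. Sample size and the first-course MTD determination do not change.

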#### 4.1.5 Blinding and procedures for unblinding

#### 4.1.5.1 Blinding

This phase I trial will be performed according to an open, single arm design. It will recruit patients with relapsed and refractory CLL and active disease. This open-label trial will be handled in an open fashion by the sponsor throughout, i.e. also for the purpose of data cleaning and preparation of the analysis. The eCRF will contain information on the treatment and the dose.

4.1.5.2 Procedures for emergency unblinding

*Not applicable.* 

## 4.1.6 Packaging, labelling, and re-supply

For details of packaging and the description of the label, refer to the Investigator Site File (ISF). Medication will be delivered to the investigator's pharmacy where the total dose per patient will be prepared upon request from the investigator.

For preparation of the BI 836826 infusion solution, the content of the vial of BI 836826 will be diluted in 0.9% sodium chloride. The content of several vials may be needed for administration of the requested dose. For further details, please refer to instructions included in the ISF.

## 4.1.7 Storage conditions

BI 836826 has to be stored in a limited access area at the temperature indicated on the trial drug label. If the storage conditions are found to be outside the specified range, immediately contact the local clinical monitor or the CRA as provided in the list of contacts. For more details on BI 836826, please refer to the IB (U10-1892-01) and the ISF.

## 4.1.8 Drug accountability

Drug supplies, which will be provided by the sponsor or a CRO appointed by the sponsor, must be kept in a secure, limited access storage area under the storage conditions defined by the sponsor. A temperature log must be maintained to make certain that the drug supplies are stored at the correct temperature.

The investigator and/or pharmacist will receive the investigational drugs delivered by the sponsor when the following requirements are fulfilled:

- approval of the study protocol by the IRB / ethics committee,
- availability of a signed and dated clinical trial contract between the sponsor and the Head of Trial Centre,
- approval/notification of the regulatory authority, e.g. competent authority,
- availability of the curriculum vitae of the principal investigator,

• availability of a signed and dated clinical trial protocol or immediately imminent signing of the clinical trial protocol,

The investigator and/or pharmacist must maintain records of the product's delivery to the trial site, the inventory at the site, the use for each patient, and the return to the sponsor or alternative disposition of unused product(s). The investigator / pharmacist will maintain records that document adequately that the patients were provided the doses specified by the CTP and reconcile all investigational product(s) received from the sponsor.

## 4.2 CONCOMITANT THERAPY, RESTRICTIONS, AND RESCUE TREATMENT

## 4.2.1 Rescue medication, emergency procedures, and additional treatments

Rescue medication to reverse the action of BI 836826 is not available. Potential side effects of BI 836826 have to be treated symptomatically. Patients should receive supportive care according to local guidelines regarding treatment of infusion-related reactions, blood product support, antibiotics, antivirals, analgesics, skin and mouth care, etc. In the case of a tumour lysis syndrome, supportive therapy including rasburicase may be used as clinically indicated at the investigator's discretion. The use of growth factors such as granulocyte colony stimulating factor (G-CSF) will be allowed, but growth factors should be avoided in the first treatment course for better assessment of safety and response parameters.

CMV reactivation during treatment should be treated according to local standards or available guidelines (R10-4431).

All concomitant non-antileukaemia therapies to provide adequate care may be given as clinically necessary. All concomitant treatments should be recorded in the eCRF except for vitamins or nutrient supplements. Trade name, indication and dates of administration of concomitant therapies will be documented. For parenteral nutrition during the trial, the components need not to be specified in detail. It should just be indicated as 'parenteral nutrition'. If a patient needs anaesthesia, it will be sufficient to indicate 'anaesthesia' without specifying the details.

Concomitant therapy should be recorded in the eCRF during the screening and treatment period, starting at the date of signature of informed consent, and ending at the EOT-visit. After the EOT-visit, only concomitant therapy indicated for treatment of an adverse event has to be reported.

## 4.2.2 Restrictions

#### 4.2.2.1 Restrictions regarding concomitant treatment

Prior antileukemia therapy must have been discontinued **in line with the requirement per exclusion criterion 1** and the patient must have recovered from all clinically relevant reversible toxicities. A time interval of at least 4 weeks must have elapsed from the last administration of any other investigational treatment for CLL to the first administration of BI 836826.

No anti-neoplastic therapy concomitantly is allowed.

Short term glucocorticoid medications may be used as clinically indicated to treat infusionrelated reactions at any dose. Daily oral steroid treatment may be administered at doses equivalent to prednisolone 20 mg per day. All other indications for steroids have to be discussed and agreed upon between investigator and sponsor.

Immunoglobulins should be avoided during treatment with BI 836826. However, if medically indicated, e.g. for substitution of immunoglobulin deficiency, immunoglobulins may be used. Administration within a time window of 2 days before and after the infusion of BI 836826 should be avoided.

4.2.2.2 Restrictions on diet and life style

No restrictions apply with regard to diet or life style.

## 4.3 TREATMENT COMPLIANCE

BI 836826 will be administered as a single intravenous infusion under supervision of the investigator or dedicated clinic personnel.

Any discrepancies will be explained in the CRF by the investigator or his/her deputy.

## 5. VARIABLES AND THEIR ASSESSMENT

## 5.1 EFFICACY - PHARMACODYNAMICS

#### 5.1.1 Endpoints of efficacy

The efficacy endpoints will be assessed at the time points specified in the Flow Chart. Efficacy endpoints will be secondary or further endpoints in this trial.

Secondary endpoints of efficacy are:

- Number of lymphocytes in the peripheral blood
- •
- Blood counts (red blood cells, haemoglobin, platelets, neutrophils)
- Best overall response according to IWCLL criteria (R10-4429)
- Progression free survival
- Failure free survival

## 5.1.2 Assessment of efficacy

5.1.2.1 Number of lymphocytes in the peripheral blood

In most patients with relapsed or refractory CLL, malignant B-cells represent the majority of lymphocytes in the peripheral blood. Reduction of B-cells can be assessed in the peripheral blood by blood cell counts, differential WBC analysis and flow cytometry, which will be performed at the time points specified in the Flow Chart.

